#### 3.2. Secondary Effectiveness Endpoints

The following secondary effectiveness endpoints will be described and compared between the two treatment arms:

1. The first secondary effectiveness endpoint will be an assessment of the mRS shift from baseline at 90 days ( $\pm$  15 days) following the study index procedure.
2. The second secondary effectiveness endpoint will be an assessment of the proportion of patients who achieve reperfusion measured using the expanded Thrombolysis in Cerebrovascular Infarction index (eTICI). Successful achievement of the endpoint is defined as achieving an eTICI score of 2b50 or greater [eTICI 2b50-3] in the target vessel following three or less passes of the randomized device (as adjudicated by Core Lab).
3. The third secondary effectiveness endpoint will be an assessment of the proportion of patients who achieve a successful First Pass Effect. Successful achievement of the endpoint is defined as achieving an eTICI First Pass Effect (FPE) defined as eTICI 2c-3 after a single pass (as adjudicated by Core Lab).
4. The fourth secondary effectiveness endpoint will be an assessment of the proportion of patients who achieve a successful Modified First Pass Effect. Successful achievement of the endpoint is defined as achieving an eTICI Modified First Pass Effect (mFPE) defined as eTICI 2b50-3 after a single pass (as adjudicated by Core Lab).
5. The fifth secondary effectiveness endpoint will be an assessment of the proportion of subjects with Early Response defined as a NIHSS drop of  $\geq 10$  points from baseline or NIHSS score 0 or 1 at seven (7) days (-2/+3 days) or discharge, whichever is sooner.

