##### **6.8.3.1. Procedural Angiography**

- Per Pass angiogram(s)
  - Obtained immediately after completion of each and every Envi™-SR, Control Device, and/or additional therapy pass
- Post-assigned device use angiogram
  - After the final assigned device use
- Post-procedure angiogram after all treatments (if different than post-assigned device use angiogram)
  - The final post procedure angiogram should comprise a full A-P lateral image.

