### 8.3.2. Analysis of the Secondary and Tertiary Endpoints

If non-inferiority is achieved based on the primary endpoint, a hierarchical step-down approach will be used to test the secondary endpoints in rank order. The following secondary effectiveness endpoints will be compared between the two treatment arms:

1. The first secondary effectiveness endpoint will be an assessment of the mRS shift from baseline at 90 days ( $\pm 15$  days) following the study index procedure. The Cochran–Mantel–

Haenszel test will be used to derive the 95% confidence intervals for the overall odds ratio. If the 95% confidence intervals for the overall odds ratio does not contain 1, the conclusion will be that the mRS shift is not proportional between the 2 devices. This is a 2-sided evaluation of the odds ratio.

2. The second secondary effectiveness endpoint will be an assessment of the proportion of patients who achieve reperfusion measured using the expanded Thrombolysis in Cerebrovascular Infarction index (eTICI). Successful achievement of the endpoint is defined as achieving an eTICI score of 2b50 or greater [eTICI 2b50-3] in the target vessel following three or less passes of the randomized device (as adjudicated by Core Lab). If the lower bound of the 1-sided 97.5% confidence interval of the difference (Envi™-SR minus Control) in the proportion of patients with eTICI 2b50 or greater flow in the target vessel post-procedure is numerically greater than -12.1%, Envi™-SR will be considered non-inferior to Control. This is a 1-sided evaluation to establish non-inferiority.
3. The third secondary effectiveness endpoint will be an assessment of the proportion of patients in whom a successful First Pass Effect is achieved. Successful achievement of the endpoint is defined as achieving an eTICI First Pass Effect (FPE) defined as eTICI 2c-3 after a single pass (as adjudicated by Core Lab). If the lower bound of the 1-sided 97.5% confidence interval of the difference (Envi™-SR minus Control) in the proportion of patients with eTICI 2c or greater flow in the target vessel post- first pass is numerically greater than -12.1%, Envi™-SR will be considered non-inferior to Control. This is a 1-sided evaluation to establish non-inferiority.

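### Section 8.3.2 item 2 contradicts itself: success is defined after at most three passes of the randomised device, but the non-inferiority rule tests flow post-procedure

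*Combined protocol and SAP*

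**What the plan says.** Section 8.3.2 item 2 has two operative sentences. The first defines success as eTICI 2b50-3 "in the target vessel following three or less passes of the randomized device (as adjudicated by Core Lab"). The second is the decision rule: a one-sided 97.5% lower confidence limit for the difference in the proportion with "eTICI 2b50 or greater flow in the target vessel post-procedure is numerically greater than -12.1" per cent leads to a declaration of non-inferiority.

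The synopsis and Section 3.2 give the same definition as the first sentence. In Section 8.2, under Additional Estimates, the sample size for this outcome also assumes a maximum of three passes.

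Section 6.8.3.1 asks for two separate images at the end of treatment. One is the post-assigned-device angiogram, taken "After the final assigned device use". The other is the "Post-procedure angiogram after all treatments (if different than post-assigned device use angiogram"). Section 3.5 permits additional therapy after three passes, or earlier with a valid exception, including when flow is still below eTICI 2b50.

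**The concern.** The two sentences can classify the same subject differently. Take a subject whose vessel is not opened in three passes of the randomised device but is then opened by additional therapy. That subject is a failure under the definition. Under the rule, if post-procedure carries its Section 6.8.3.1 meaning, the subject is a success.

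The primary derivation of the primary endpoint (Method 1) ignores additional therapy, and the first secondary endpoint is also based on the 90-day mRS. Item 2 is therefore the first test in the hierarchy that looks at what the randomised device itself achieves. Scored on the final angiogram, it would measure the device plus rescue. Any rescue that works equally well in both arms pulls the two rates together, which in a non-inferiority test favours a positive result.

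The ambiguity also leaves two defensible programs for one confirmatory test. That choice should be closed before anyone sees outcome data.

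**Working it through.** **Wording, side by side.** The rule for item 3 tests "eTICI 2c or greater flow in the target vessel post- first pass is numerically greater than -12.1" per cent, and item 4 likewise says first pass. Both keep the timepoint of their own definitions. Item 2 is the only one of the three eTICI rules that does not.

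**Inputs from the documents.** Expected rate about 74% in both arms, planning margin 12.2%, 80% power, one-sided 2.5%, stated total 408 (Section 8.2, Additional Estimates). Decision margin 12.1% (Section 8.3.2). Target 270 and maximum 448 ITT subjects, allocated 1:1, so 135 or 224 per arm.

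**Inputs assumed.** The documents do not say how many randomised-device failures receive additional therapy or how often it succeeds. Let r be the share of all failures brought to eTICI 2b50 or better by additional therapy, equal in both arms. Then r = 0.25 means, for example, half treated and half of those opened; r = 0.70 means all treated and 70% opened.

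**Reproducing the plan's figure.** n per arm = 2 × 0.74 × 0.26 × (1.960 + 0.842)² / 0.122² = 202.9, so 203 per arm and 406 in total. The Farrington-Manning variance gives 203.3, so 204 per arm and 408 in total, an exact match. With the decision margin of 12.1% the total is 414. The 12.1/12.2 difference is small but should be reconciled at the same time.

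**Effect of the literal reading.** Take a device exactly at the margin: 74.0% − 12.1 points = 61.9%.

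- Control after rescue: 0.74 + 0.26r
- Envi-SR after rescue: 0.619 + 0.381r
- Difference: −0.121 × (1 − r)
- P(pass) = Φ[(difference + 0.121)/SE − 1.96], with SE the unpooled standard error

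For r = 0.50 at 135 per arm, the rates are 0.870 and 0.8095 and SE = √[(0.870 × 0.130 + 0.8095 × 0.1905)/135] = 0.0445. Then (−0.0605 + 0.121)/0.0445 − 1.96 = −0.60, so P = 27%.

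| r | Control | Envi-SR | Difference (points) | P(pass), 135 per arm | P(pass), 224 per arm |
|---|---|---|---|---|---|
| 0 | 74.0% | 61.9% | −12.1 | 2.5% | 2.5% |
| 0.25 | 80.5% | 71.4% | −9.1 | 8.5% | 11.4% |
| 0.50 | 87.0% | 80.95% | −6.05 | 27% | 42% |
| 0.70 | 92.2% | 88.6% | −3.6 | 66% | 86% |

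Summing exact binomial probabilities for the same Wald limit at 135 per arm gives 28% for r = 0.50 and 66% for r = 0.70, so the approximation is adequate. The row r = 0 is also the result under the definition, where rescue does not count: the test then holds its nominal 2.5%.

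**The case against.** The strongest reply is that the definition controls. It stands in the sentence immediately before the rule, and the same timepoint appears in the synopsis, Section 3.2 and the sample-size text. Against these stands one word. Post-procedure is also not a defined term: Section 6.8.10 uses it as the heading for all visits from 24 hours to 90 days, Section 6.9 uses it for the 24-hour imaging, and the item 2 rule names no angiogram. This part of the reply stands. A reader might infer from the rule that the trial counts rescue with other devices as success for the randomised device. The documents do not support that; they support only that the rule, taken literally, would do so.

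A reader might also infer that an inferior retriever could pass unnoticed. That goes too far. Items 3 and 4 score reperfusion after a single pass with correctly worded rules. Methods 2 and 3 treat additional therapy for reperfusion failure as failure of the primary endpoint. The number of passes to eTICI 2b50 is an exploratory endpoint. A device that failed more often should show up in these results, although none of them repairs item 2.

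Finally, the probabilities depend on assumed rescue rates and apply to this test taken alone. Item 2 is tested only if the primary endpoint is met, and it comes after the first secondary endpoint in rank order. The chance of an actual false claim cannot exceed the tabulated figures and may be lower.

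What the reply does not remove is the contradiction itself, in the one sentence that produces the verdict.

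**Conclusion.** The point holds as an internal inconsistency between definition and decision rule in Section 8.3.2 item 2. If the rule is applied literally, a true device difference of 12.1 points shrinks to between 9.1 and 3.6 points as r goes from 0.25 to 0.70. The chance of passing this test at 135 per arm then rises from 2.5% to about 9% to 66%. This rests on a device exactly at the margin, a 74% control rate, equal rescue in both arms, and rescue rates that the documents do not give. Only the direction is independent of the chosen rate: with equal rescue, any r above zero dilutes the difference.

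Analysis detail is referred to a SAP whose separate text is not in the file reviewed, so the programmed derivation could not be checked. The severity is that of a wording correction to a gated secondary endpoint. Design, sample size and data collection are unaffected.

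**What to change.** In the decision rule of Section 8.3.2 item 2, delete post-procedure and use the definition's own timepoint, "in the target vessel following three or less passes of the randomized device". State that the outcome is scored on the Core Lab-read angiogram after the last randomised-device pass (at most three) and before any additional therapy, that is, the post-assigned-device image of Section 6.8.3.1. Report the final post-procedure eTICI by arm as a descriptive result. Carry the same wording into the SAP and its programming specification before unblinding, and use one margin, 12.1% or 12.2%, in both the rule and the sample-size text.

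The cost is editorial. Section 6.8.3.1 already requires an angiogram after every pass and after the last use of the assigned device, and Section 6.9 already has the Core Lab read eTICI on each device pass. The reported success rate may be lower than the final post-procedure rate, as the definition implies.

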### 8.3.3. Subject Analysis Populations

The following populations have been defined for reconciliation and analysis: the Enrolled population, ITT (Intention to Treat) population, PP (Per Protocol) population, and the As-Treated populations.

See section 5.1 Enrollment for descriptions of the populations.

#### **8.3.4. Evaluating the Effect of Different Clinical Sites and Regions (US vs. OUS) and the Effect of Clinical Sites with Low Patient Enrollment**

The method to be applied for examining the effect of different clinical sites will facilitate the generation of adjusted estimates to contrast against the unadjusted estimates. The adjusted estimates for the primary effectiveness and safety endpoints will introduce the effect of different clinical sites; the unadjusted estimates for the primary effectiveness and safety endpoints will only consider the randomized treatment assignment in the model. This sensitivity analysis will address the fundamental question relative to the effect of clinical sites and is considered more informative than simply adding an interaction term into the model for analysis. To provide further insight into the results, the model will be run with the interaction term retained for treatment and clinical site.

To assess the effect of small clinical sites, sites with lower enrollment will be defined as having  $\leq 2$ , 3, 4, 5, and 6 patients. For each dataset with small sites defined as having  $\leq 2$ , 3, 4, 5, and 6 patients, a random effects model will be used to calculate the overall estimate adjusted by clinical site. The general framework of the random effects model will adjust for variability both among the clinical sites and variability within the clinical sites. The model that will be used to derive the estimates and the standard errors is presented in the SAP. This model will be used to assess the primary effectiveness and safety endpoints. From the solution for fixed effects, the exponentiation of the estimates and the standard errors will provide adjusted confidence limits to assess the effect adjusted for clinical sites.

To assess the effect of geographic location, a random effect model will be used to calculate the overall estimate adjusted by the location of the investigational site (US vs. OUS). The model that will be used to derive the estimates and the standard errors is presented in the SAP. This model will be used to assess the primary effectiveness and safety endpoints. From the solution for fixed effects, the exponentiation of the estimates and the standard error will provide adjusted confidence limits to assess the effect adjusted for geographic location.

The testing strategy and exact model for analysis will be included in the Statistical Analysis Plan (SAP).

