#### **8.3.5. Evaluating the Effect of Different Control Devices**

The method to be applied for examining the effect of different control devices will facilitate the generation of adjusted estimates to contrast against the unadjusted estimates. The adjusted

estimates for the primary effectiveness and safety endpoints will introduce the effect of different control devices; the unadjusted estimates for the primary effectiveness and safety endpoints will only consider the randomized treatment assignment in the model. This sensitivity analysis will address the fundamental question relative to the effect of the different devices and is considered more informative than adding an interaction term into the model for analysis. To provide further insight into the results, the model will be run with the interaction term retained for treatment and different control devices.

To assess the effect of different control devices used in the control arm of the study, a random effects model will be used to calculate the overall estimate adjusted for each of the 2 device types (Trevor and Solitaire). The model that will be used to derive the estimates and the standard errors is presented in the SAP. From the solution for fixed effects, the exponentiation of the estimates and the standard error will provide adjusted confidence limits to assess the effect.

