### **8.3.7. Evaluating the Effect of Time Last Seen Well (0-6 hours and >6 to 24 hours)**

The method to be applied for examining the effect of time last seen well (TLSW) will facilitate the generation of adjusted estimates to contrast against the unadjusted estimates. The adjusted estimates for the primary effectiveness and safety endpoints will introduce the effect of the time last seen well (0-6 hours and >6 to 24 hours); the unadjusted estimates for the primary effectiveness and safety endpoints will only consider the randomized treatment assignment in the model. This sensitivity analysis will address the fundamental question relative to the effect of the time last seen well (0-6 hours and >6 to 24 hours) and is considered more informative than adding an interaction term into the model for analysis. To provide further insight into the results, the model will be run with the interaction term retained for treatment and time last seen well (0-6 hours and >6 to 24 hours).

To assess the effect of the time last seen well (0-6 hours and >6 to 24 hours), a random effects model will be used to calculate the overall estimate adjusted for the discrete time segments. The model that will be used to derive the estimates and the standard errors is presented in the SAP. From the solution for fixed effects, the exponentiation of the estimates and the standard error will provide adjusted confidence limits to assess the effect.

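### Region, control-device family and time-window models: the confidence limits are misdescribed, a two-level random effect would reveal little heterogeneity, and no treatment-by-region interaction is named

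*Combined protocol and SAP*

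**What the plan says.** Section 8.3.4, on US versus non-US sites: "To assess the effect of geographic location, a random effect model will be used to calculate the overall estimate adjusted by the location". Section 8.3.5, on control devices: "a random effects model will be used to calculate the overall estimate adjusted for each of the 2 device types", namely Trevo and Solitaire. Section 8.3.7, on time last seen well: "a random effects model will be used to calculate the overall estimate adjusted for the discrete time segments", of which there are two.

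The limits are described in the same way each time; in Section 8.3.4, "From the solution for fixed effects, the exponentiation of the estimates and the standard error will provide adjusted confidence limits". The wording occurs twice in Section 8.3.4 (small sites and region) and again in Sections 8.3.5, 8.3.6 and 8.3.7.

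Treatment interactions are named for clinical site (8.3.4), control device (8.3.5), Envi-SR size (8.3.6) and time window (8.3.7). None is named for region. Section 6.10.1 says poolability across geographies will be judged on the criteria in Section 8 and the SAP.

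The full model is deferred: "The testing strategy and exact model for analysis will be included in the Statistical Analysis Plan (SAP". The site analysis is given sensitivity status: "This sensitivity analysis will address the fundamental question relative to the effect of clinical sites".

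**The concern.** There are four separate difficulties.

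- **Limits.** A confidence limit for an odds ratio is the exponential of the estimate plus or minus a multiple of its standard error. Exponentiating the standard error by itself gives no limit. A programmer following the text literally would print wrong intervals.
- **Two levels.** If region, family or window is itself the random term, its variance is estimated from two values, on one degree of freedom. When that estimate is zero, the adjusted result reproduces the unadjusted one, and the agreement says little about heterogeneity.
- **Region.** Poolability turns on whether the treatment effect differs between US and non-US sites. The only region analysis that Section 8 names yields an overall adjusted estimate, with no treatment-by-region term.
- **Control family.** Trevo and Solitaire are used only in the control arm, so a treatment-by-family interaction has no data in the other arm.

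At stake is how far the sensitivity and poolability analyses can support pooling.

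**Working it through.** **Inputs.** From Section 8.2: 46% control and 50.5% Envi-SR success, 135 per arm, margin -12.5 points. One-sided 2.5% and 80% power are stated for the 426-subject calculation and assumed for the 270-subject one. Not in the documents, so assumed: the split between levels (70/30 unless stated) and between-level SDs of 0 to 0.4 on the logit scale.

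**1. The plan's own figure.** n per arm = (1.960 + 0.842)² × (0.46×0.54 + 0.505×0.495) / (0.125 + 0.045)² = 7.85 × 0.4984 / 0.0289, about 135.4, so 136 per arm or 272 in total, against 270 stated (power at 270 is 79.9%). The inputs are consistent. The plan gives no figure for the random-effects analyses.

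**2. Limits.** At 46% in both arms, SE(log OR) = √(2/(135×0.46×0.54)) = 0.244 and exp(0.244) = 1.28. For OR 0.90, log OR = -0.105; correct limits are exp(-0.105 ± 1.96×0.244) = 0.56 to 1.45.

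At the planning rates, log OR = 0.180, SE = 0.244, OR = 1.198:

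| Reading | Result |
|---|---|
| exp(b ± 1.96·SE) | 0.743 to 1.931 |
| exp(b) ± 1.96·exp(SE) | -1.30 to 3.70, impossible for an odds ratio |
| exp(b ± SE) | 0.94 to 1.53, about 68% coverage |

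**3. Variance from two levels.** On 1 df the 95% interval for an SD runs from √(1/χ²(0.975)) = 0.45 to √(1/χ²(0.025)) = 31.9 times the estimate. With 30 levels, as for the maximum number of sites, it is 0.80 to 1.34 times.

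Random intercept (levels differ in outcome rate), maximum likelihood, 600 simulated trials per setting:

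| True SD | SD estimated as zero | Treatment coverage, random | Treatment coverage, fixed | Mean SE, random / fixed |
|---|---|---|---|---|
| 0 | 89% | 94.7% | 94.7% | 0.2449 / 0.2452 |
| 0.2 | 73% | 95.2% | 95.0% | 0.2459 / 0.2464 |
| 0.4 | 47% | 95.0% | 94.7% | 0.2498 / 0.2505 |

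Monte Carlo error on coverage is about 0.9 points. A moment estimator gives fewer zeros: 49% to 54% at SD 0.2 and 31% to 37% at SD 0.4, for splits of 135/135 and 220/50.

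Random treatment effect (levels differ in treatment effect, the question for pooling): the moment estimate is zero when Q < 1, and P(Q < 1) = P(χ²₁ < (V₁+V₂)/(V₁+V₂+2τ²)). With 94 and 41 per arm in the two levels, V₁ = 2/(94×0.25) = 0.085 and V₂ = 2/(41×0.25) = 0.195. This gives 62% at τ = 0.2 and 51% at τ = 0.4; 40,000 simulated trials gave 62.5% and 50.2%. Coverage of the usual normal limits was 96.3%, 95.5%, 93.4% and 87.0% at τ = 0, 0.1, 0.2 and 0.4.

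**4. Control-device interaction.** There are three observable groups: control with Trevo, control with Solitaire, and Envi-SR. A treatment-by-family interaction needs four. Three group means support two contrasts, Envi-SR against each family. The difference between those contrasts is simply Trevo against Solitaire among controls.

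**The case against.** The strongest reply is that the protocol does not fix the model. Sections 8.3.4, 8.3.5 and 8.3.7 refer it to the SAP, and the model is not in the text reviewed here. Taking estimates from the fixed-effects solution is compatible with region or window being fixed and site random. This stands: the two-level criticism is conditional on which term is random.

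The limit wording may also be shorthand for the usual formula. That is plausible, but it recurs in four sections and takes one phrase to correct.

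A reader might infer that the two-level random effect itself makes the treatment limits wrong. The simulation does not support that for a random intercept. Only a random treatment effect degrades them, and the documents do not specify one. Nor do the intercept results show that heterogeneity of treatment effect is being hidden, since they concern outcome rates.

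A reader might also infer that these odds ratios will be judged against -12.5%. No section does so; they are contrasted with unadjusted estimates. Finally, part of the remedy already exists. Section 8.3.7 plans a treatment-by-window interaction, and Section 8.3.1 plans a logistic model with the stratification variables, including onset time, and unspecified subgroup analyses. The gap is region.

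**Conclusion.** The point holds in limited form. Read literally, the limit formula is wrong in every place it appears. If a two-level factor is the random term, its variance is close to inestimable, and agreement between adjusted and unadjusted results would be weak evidence of homogeneity. The zero-estimate rates depend on the assumed SD, split and estimator. The missing treatment-by-region interaction and the non-estimable control-device interaction do not depend on those assumptions. The latter could change only if the control family intended for each subject were recorded before randomization, and I found no such step.

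The primary non-inferiority test, a risk difference against -12.5%, is unaffected. The documents also do not support reading Section 8.3.7 as deciding whether time windows may be pooled: Section 6.10.1 speaks of poolability only for geographies, and Section 8.3.7 is labelled a sensitivity analysis.

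**What to change.** In Section 8.3 and the SAP:

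- Enter region and time window as fixed factors and keep random effects for site. State which terms are random.
- Add a fixed treatment-by-region interaction; the window interaction is already planned.
- Report region- and window-stratified risk differences with 95% confidence intervals, on the scale of the primary margin. Mantel-Haenszel weighting is one option.
- Write the limits as exp(estimate ± 1.96·SE) in Sections 8.3.4 (both places), 8.3.5, 8.3.6 and 8.3.7.
- Replace the control-device interaction with a descriptive comparison of Envi-SR with each control family. Label it non-randomized and confounded with time window, because Section 6.2 permits only Trevo at 16-24 h.

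For region, window and the limits, the cost is wording and simpler code; in the simulation, fixed-factor coverage was 94.7% to 95.0%. Two limitations remain. The control-family comparison cannot be made causal by relabelling. The region interaction will be imprecise: at a 70/30 split its SE is √(0.085 + 0.195) = 0.53, so only a ratio of odds ratios beyond about exp(1.96×0.53) = 2.8 would reach two-sided 5%. It should therefore be reported as an estimate with its interval, without treating a non-significant result as proof of poolability.
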